11.3 Appendix 3: Treatment States and Phases

11.3.1 Treatment Phases

Assessments and events will be classified according to the time of occurrence relative to dosing.

Treatment Phase	Definition
Pre-Treatment	Date/Time < Study Treatment Start Date/Time
On-Treatment*	Study Treatment Start Date/Time ≤ Date/Time ≤ Study Treatment Stop Date/Time+7
Post-Treatment*	Date/Time+7 > Study Treatment Stop Date/Time

NOTES:

- * Treatment phase assumes that the effects of study treatment duration will last a week.
- Study Treatment Start relates to the 1st dose received by the individual and the Study Treatment Stop relates to the final dose received by the individual

11.3.2 Treatment States

Assessments and events will be classified according to time of occurrence relative to the start and/or stop date of the study treatment.

11.3.2.1 Treatment States for AE (and DRE) Data

Treatment State	Definition
Pre-Treatment	AE Start Date/Time < Study Treatment Start Date/Time
On-Treatment*	If AE onset date/time is on or after treatment start date/time & on or before treatment stop date/time. Study Treatment Start Date/Time ≤ AE Start Date/Time ≤ Study Treatment Stop Date/Time + 7
Post-Treatment*	If AE onset date is after the treatment stop date. AE Start Date > Study Treatment Stop Date + 7
Onset Time Since 1 st Dose (Days)	If Treatment Start Date > AE Onset Date = AE Onset Date – Treatment Start Date If Treatment Start Date ≤ AE Onset Date = AE Onset Date – Treatment Start Date + 1 Missing otherwise.
Duration (Days)	AE Resolution Date – AE Onset Date + 1
Drug-related ^Δ	If relationship is marked 'YES' on eCRF OR value is missing

NOTES:

- * Treatment phase assumes that the effects of study treatment duration will last a week.
- Study Treatment Start relates to the 1st dose received by the individual and the Study Treatment Stop relates to the final dose received by the individual. If the study treatment stop date is missing then the AE will be considered to be On-Treatment.
- Δ=Not applicable/required for DRE

11.3.2.2 Treatment States for CRS Events Data

Treatment State	Definition
Pre-Treatment	CRS Start Date/Time < Study Treatment Start Date/Time
On-Treatment Week i i=1, 2, 3, ..., 7	If CRS Start Date/Time is on or after i^{th} dose of treatment start date/time & on or before $(i+1)^{th}$ dose of treatment stop date/time. I^{th} Study Treatment Dose Start Date/Time \leq CRS Start Date/Time \leq $(i+1)^{th}$ Study Treatment Start Date/Time
Post-Treatment*	If CRS onset date is after the last dose of treatment start date/time + 7 ie, CRS Start Date/Time > Study Treatment Stop Date/Time + 7.
Onset Time Since 1 st Dose (Days)	If Treatment Start Date > CRS Onset Date = CRS Onset Date – Treatment Start Date If Treatment Start Date \leq CRS Onset Date = CRS Onset Date – Treatment Start Date + 1 Missing otherwise.
Duration (Days)	CRS Resolution Date – CRS Onset Date + 1
Drug-related	If relationship is marked 'YES' on eCRF OR value is missing

NOTES:

- * Treatment phase assumes that the effects of study treatment duration will last a week.
- If the study treatment stop date is missing then the CRS event will be considered to be On-Treatment during Week 1.

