Sputum induction and processing for BAC associated sample collection							X	Sputum sample is conditional on having obtained a sputum sample from the subject at screening. Perform sputum induction after collection of 24 hour post-dose DV8 blood and nasal samples (as pre BAC sample for FUV1).
Follow up phone call						X 	X 	
 Following at least the first two doses of study treatment to assess tolerability
 
 On DV 2, 3, and 5-7, a follow-up phone call will be made approximately 24 hours post-dose to check if any CRS events have occurred, and if they have, that they have been accurately recorded in the diary card and they will then be transcribed into the eCRF.
 
For DV1, 4 and 8 the subjects shall be assessed on their return to the unit the following day.

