Chills/Rigors	Shivering & trembling	Chills (10008531) Feeling cold (10016326)
Nausea	Feeling sick	Nausea (10028813)
Vomiting	Being sick	Vomiting (10047700)
Diarrhoea	Loose stools & frequent bowel movements	Diarrhoea (10012735)
Arthralgia	Arthralgia	Arthralgia (10003239) Musculoskeletal stiffness (10052904)
Myalgia	Achy Muscles	Myalgia (10028411) Back pain (10003988) Neck pain (10028836) Pain (10033371) Pain in extremity (10033425)
Hypotension	Low blood pressure	Hypotension (10021097)

Note: The above may not be an exhaustive list. Therefore, prior to unblinding the medical monitor shall review a list of distinct AE preferred terms observed in the study and ensure that they are all assigned/mapped to a single CRS category (if the preferred term does not relate to a CRS category then it can be mapped as non-CRS; further queries may be raised with the sites if a term was not marked by the site as a CRS event but maps to a CRS category via its MEDDRA coding).

- In the event that multiple terms with different CRS grading scores are mapped to the same CRS category the worst case score (highest severity) should be used in any TLFs.
- For each CRS category the total number of occasions (visits) each subject experienced any non-zero grade of CRS event should be derived (should range between 0 and 8 if the subject completed all dosing visits as planned). This should also be expressed as a proportion of the actual dosing visits attended by the subject.
- For each subject and dosing visit combination the number of different CRS event categories should be derived (where the subjects reported any non-zero grade event); e.g. Subject P experienced 3 different CRS event types at dosing visit 1, 0 CRS event types at dosing visit 2, 4 CRS event types at dosing visit 3, etc.

Rescue Medication

[figure not shown]
Rescue medication (e.g. Salbutamol) administered as part of the BAC procedures will not be reported separately (it may be reported as part of the con med listings).

Prior to DBF the medical monitor should review the unique medications in the con med dataset to flag any items that should be classified as rescue medications.

Laboratory Parameters

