11.13.8 Safety Figures

Safety: Figures					
No.	Population	IDSL / TST ID / Example Shell	Title	Programming Notes	Deliverable [Priority]
PEF					
3.1.	All Subjects	Figure 10.107 TL7116958	Unadjusted Mean Peak Expiratory Flow vs Time Profiles by Treatment (with approx 95% CI Bands)	Display the raw Treatment means for each day and connect each (1 st page uses main treatment descriptors and 2 nd page uses Alternative descriptors). Do not add individual CIs for each day, but instead display them as a band plot. X-axis is continuous (Week) with tick marks every 7 days (1 st Dose is Week 0) Add vertical reference lines for the 1 st and 8 th planned dose	FSP: SAC [2]
3.2.	All Subjects	Figure 10.107 TL7116958	Unadjusted Mean AM Peak Expiratory Flow vs Time Profiles by Treatment (with approx 95% CI Bands)	As per Mean PEF Figure	FSP: SAC [2]
3.3.	All Subjects	Figure 10.107 TL7116958	Unadjusted Mean PM Peak Expiratory Flow vs Time Profiles by Treatment (with approx 95% CI Bands)	As per Mean PEF Figure	FSP: SAC [2]

Safety: Figures					
No.	Population	IDSL / TST ID / Example Shell	Title	Programming Notes	Deliverable [Priority]
3.4.	All Subjects	SAFE_F1	Frequency of Cytokine Release Syndrome Events (within individuals) over the Eight Planned Dosing Visits	
Try to get all CRS events on one page. Do not distinguish between CRS severity grades in this display.
 
1st Page should be Placebo and 20ng treatments (two bars per CRS category)
 
2nd Page should use Placebo/Allergen stratum combinations (four bars per CRS category)
 
Footnote each subsection of each bar when individuals did not complete all 8 visits fall.
 
If possible consider patterns/fill types that can display in black and white (but revert to example shell (colours only) if patterns result in confusing figure details)
	SAC [1]

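### The CRS treatment-state rule gives no week or state to events in the 7 days after a subject's last dose, and puts every CRS event in Week 1 if the stop date is missing

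*SAP*

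**What the plan says.** SAP section 11.3.2.2 (Appendix 3) gives each CRS event one of three kinds of state:

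- Pre-Treatment, for onset before the first dose.
- An on-treatment week, in a row headed "On-Treatment Week i i=1, 2, 3, ..., 7". Week i runs from dose i to dose i+1, with both ends included.
- Post-Treatment, defined by "CRS Start Date/Time > Study Treatment Stop Date/Time + 7" (days).

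A note to the table adds: "If the study treatment stop date is missing then the CRS event will be considered to be On-Treatment during Week 1".

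The meaning of stop comes from the adverse event table in section 11.3.2.1: "Study Treatment Stop relates to the final dose received by the individual". That table carries On-Treatment through stop plus 7 days. Its own missing-date note names no week: "If the study treatment stop date is missing then the AE will be considered to be On-Treatment". SAP section 11.2.1 directs that the section 11.3.2 algorithms be used for CRS assignment.

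Other places expect CRS after all eight doses. SAP section 11.5.3 derives, for each CRS category, a per-subject count of visits with CRS, which "should range between 0 and 8 if the subject completed all dosing visits as planned". Figure 3.4 in SAP section 11.13.8 is titled "Frequency of Cytokine Release Syndrome Events (within individuals) over the Eight Planned Dosing Visits". Protocol section 7.1.2, describing the next-day CRS check, says: "For DV1, 4 and 8 the subjects shall be assessed on their return to the unit the following day".

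**The concern.** A week exists only if another dose follows it, and the index stops at 7. Nothing covers the time between the last dose and 7 days after it. That is the interval after dose 8 in a completer, and the interval after dose k in a subject who stops after k doses. Protocol section 7.4.1.7 limits CRS to symptoms in the 24 hours after a dose, so the events affected are those provoked by the last dose.

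The missing-stop note is a separate fault. The week of an event depends on its onset and the dose times, and protocol section 6.6 has the date and time of each clinic dose recorded. Placing the event in Week 1 makes a late reaction look like a first-dose reaction. Timing is informative for this drug: protocol section 4.6.1 reports that, in the earlier 8-week study, cytokine-related fever (frequent at 80 ng, absent at 20 ng and placebo) appeared mostly after the second dosing visit.

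The output at stake is the by-week CRS summary. SAP Table 7 (section 8.2.1) marks both a table and a listing of it for production. Under section 11.3.2.2 that display would have no row for CRS after the last dose.

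**Working it through.** **Inputs.** Eight weekly doses, taken at days 0, 7, ..., 49 (dose i at day 7(i−1)). Week i = [dose i, dose i+1] for i = 1 to 7, and Post-Treatment is onset later than the last dose + 7 days (SAP 11.3.2.2). Stop is the last dose received (SAP 11.3.2.1). CRS onset is within 24 hours of a dose (protocol 7.4.1.7).

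**Against the plan's own figure.** SAP 11.5.3 expects 0 to 8 visits with CRS in a completer. Classifying an onset 12 hours after each dose by the week rule gives Weeks 1 to 7 for doses 1 to 7 and no state for dose 8. The week index therefore reaches at most 7. The 11.5.3 count itself can still reach 8 if it is built from visits.

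**Where the gap lies.**

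| Doses received | Onset with no state | Post-Treatment from | Doses whose 12-hour CRS gets a week |
|---|---|---|---|
| 8 | after day 49, to day 56 | after day 56 | 7 of 8 |
| 3 | after day 14, to day 21 | after day 21 | 2 of 3 |
| 1 | day 0 to day 7 | after day 7 | 0 of 1 |

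One detail at the boundaries: because both ends are included, an onset at exactly the time of the last of two or more doses falls in the previous week. For the same reason, in a completer, an onset exactly at any of doses 2 to 7 falls in two weeks.

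**Changing 7 to 8 alone.** Week 8 would then need a ninth dose as its upper bound, and a subject who stops early would still have no week after the last dose. A closing rule for the last dose is needed.

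**Share of dosing intervals uncovered.** Each dosed subject has exactly one uncovered interval, so the share is subjects ÷ total doses. Protocol 4.2 plans about 24 per arm, or 48 subjects.

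- All complete: 48 / (48 × 8) = 48/384 = 12.5%.
- 40 complete and 8 stop after 7 doses: 48 / (40 × 8 + 8 × 7) = 48/376 = 12.8%.
- The 8 stop after 4 doses: 48 / (320 + 32) = 48/352 = 13.6%.
- The 8 stop after 1 dose: 48 / (320 + 8) = 48/328 = 14.6%.

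The figure of 40 completers follows the target of 20 per arm in protocol 4.3. The stopping points are assumptions.

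**Missing stop date.** All events go to Week 1. In the worst case, with CRS after each of k doses, k − 1 of k events get the wrong week: 1 of 2 at k = 2 and 7 of 8 at k = 8. None is wrong if CRS follows dose 1 only.

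**Replacement rule (see the fix).** For k = 1 to 8 doses on a weekly schedule, with the stop date present or missing, CRS 12 hours after each dose gets Weeks 1 to k correctly. An onset 7 days after dose 8 is Week 8, and at 7.01 days it is Post-Treatment. Each of 20,000 onsets from day −3 to day 70 received exactly one state.

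**The case against.** The best reply is that this is a drafting slip whose intent is clear. The table's own note says treatment effects last a week. SAP sections 11.3.1 and 11.3.2.1 both keep these events On-Treatment through stop plus 7 days, so no event is lost as an adverse event. Table 7 is an overview that refers to Appendix 13 for details, and Appendix 13 lists no CRS output titled by week. Its CRS displays are an overall summary, outputs by dosing visit, and listings, none of which is shown to use the week. The mock shells are in a separate document. A missing stop date is unlikely when every dose is given in clinic and final analysis follows cleaning and freeze (SAP 3.4). The percentages count intervals rather than events. The early-stopping scenarios are also loose: the target of 20 per arm requires the follow-up allergen challenge as well, so a subject short of it may have had all eight doses.

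Most of this stands as a limit on consequence. It does not make the rule correct. Table 7 still marks the by-week CRS table and listing as produced, section 11.2.1 makes this algorithm the one to use, and the intended reading cannot be reached by correcting the index alone. The early-stopping range is illustrative; the 12.5% for completers does not depend on it.

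**Conclusion.** The concern holds, at low severity. As written, CRS that starts after a subject's last dose and within 7 days of it has no CRS week or state. This leaves 1 of 8 dosing intervals (12.5%) uncovered in every completer and 1 of k in a subject who stops after k doses. Across 48 subjects it is 12.5% if all complete, and 12.8% to 14.6% under the assumed early stopping. The number of events affected cannot be given: the documents supply no CRS counts for this trial, and protocol section 4.5 describes CRS at 20 ng as infrequent in the earlier study. The loss is confined to the CRS week or state. The missing-stop note is also wrong as written, but should seldom apply.

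**What to change.** In SAP section 11.3.2.2, run the index from 1 to 8 and state:

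> A CRS event on or after the first dose is assigned to the week of the most recent recorded dose at or before onset. The last recorded dose's week ends 7 days after that dose, and later events are Post-Treatment. Events before the first dose are Pre-Treatment.

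Replace the Week 1 note with:

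> If the study treatment stop date is missing, use the last recorded dose date/time as the stop date and apply the same rule. If the onset or dose dates needed are missing, classify the event as On-Treatment with week missing.

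The wording also removes the double assignment at exact dose times. Protocol section 5.4 allows a subject to miss a dose and continue, so the SAP should also say whether the week number counts doses received or planned visits.

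The cost is one table row, one note and a few lines of derivation code. No new data are needed.

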11.4 Appendix 4: Data Display Standards & Handling Conventions

11.4.1 Study Treatment & Sub-group Display Descriptors

Treatment Group Descriptions (Main / default)			
RandAll NG		Data Displays for Reporting	
Code	Description	Description ^[1]	Order ^[2]
A	Placebo intranasal once weekly	Placebo	1
B	GSK2245035 20ng i.n. once weekly	20 ng GSK2245035 i.n. once weekly	2

NOTES:

1. Abbreviated versions of the treatment descriptions are also permissible if space is restricted e.g., 20ng GSK2245035.
2. Order represents treatments being presented in TFL, as appropriate.

Alternative Treatment Group Descriptions #1			
RandAll NG		Data Displays for Reporting	
Description	Stratum	Description ^[1]	Order ^[2]
Placebo	Presumed Allergen	Placebo: Presumed Allergen	1
	Unknown Allergen	Placebo: Unknown Allergen	2
20 ng GSK2245035 i.n. once weekly	Presumed Allergen	20 ng GSK2245035 i.n. once weekly: Presumed Allergen	3
	Unknown Allergen	20 ng GSK2245035 i.n. once weekly: Unknown Allergen	4

NOTES:

1. Abbreviated versions of the treatment descriptions are also permissible if space is restricted e.g., 20ng GSK2245035: Pres, 20ng GSK2245035: Unk; or Pbo P, Pbo U, 20ng P, 20ng U
2. Order represents treatments being presented in TFL, as appropriate.

11.4.2 Baseline Definition & Derivations

11.4.2.1 Baseline Definitions

For all endpoints (expect as noted in baseline definitions) the baseline value will be the latest pre-dose assessment.

Parameter	Study Assessments Considered As Baseline					Baseline Used in Data Display/Analysis
	Screening Visit 1	Screening Visit 2	24H After Screening Visit 2	Day 1 Pre-dose	Pre-Dose on Corresponding Dosing Visit	
Efficacy						
LAR Minimum FEV ₁		X				Screening Visit 2
LAR: WM FEV ₁		X				Screening Visit 2
EAR Minimum FEV ₁		X				Screening Visit 2
EAR: WM FEV ₁		X				Screening Visit 2
Laboratory						
Chemistry				X		Day 1 Pre-dose
Haematology				X		Day 1 Pre-dose
Safety						
ECG				X		Day 1 Pre-dose
Vital Signs (excluding body temperature)				X		Day 1 Pre-dose
Nasal Examination				X		Day 1 Pre-dose
Body Temperature					X	DV<x> Pre-Dose
Pharmacodynamic and Biomarker (including FeNO) (See Specific model details in Section 8.4.2)						
Other Exploratory Endpoints (excluding Diary Card data)						
IAC Wheal/Flare Early Phase		X (15M)				Screening Visit 2 (15M)

Parameter	Study Assessments Considered As Baseline					Baseline Used in Data Display/Analysis
	Screening Visit 1	Screening Visit 2	24H After Screening Visit 2	Day 1 Pre-dose	Pre-Dose on Corresponding Dosing Visit	
IAC Wheal/Flare Late Phase		X (6H)				Screening Visit 2 (6H)

NOTES :

1. Unless otherwise stated, the mean of replicate assessments at any given time point will be used as the value for that time point.

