#### 4.6.1. Risk Assessment

Potential Risk of Clinical Significance	Summary of Data/Rationale for Risk	Mitigation Strategy
Investigational Product (IP) [GSK2245035]		
Events potentially related to cytokine induction.	
The principal systemic effect seen with GSK2245035 in intranasal studies in animals (mice, rats, rabbits, and monkeys) up to 8 weeks in duration with weekly dosing was increases in the levels of specific cytokines; all other findings were considered to be secondary to this primary response (i.e., nasal irritancy, increased body temperature, increased heart rate, alterations in splenic and lymph node cellularity and minor changes in some clinical chemistry parameters). With the exception of the splenic and lymph node effects, all the observed changes would be readily monitorable in humans. The effects that were seen in the spleen and lymph node were of low severity and were shown to be fully reversible on withdrawal from treatment in the monkey. The observed cytokine response is consistent with the known TLR7 pharmacology of GSK2245035. Although a no effect level for cytokine response was not determined in the monkey, a No Observed Adverse Event Level (NOAEL) of 35.9 ng/kg/day was determined for the only secondary finding
	
The study will be undertaken at experienced research units. The sites have all necessary facilities to handle medical emergencies. All subjects will receive each dose in the unit and will be monitored closely after each dose (for approximately 1-2 hours). Each subject will receive a phone call approximately 12 hours following administration of at least the first two doses to assess tolerability. They will be provided with a thermometer to measure body temperature. Thorough monitoring of any AEs will be performed throughout the treatment period to allow early assessment and mitigation of risk.
 
Only subjects in good general health with a diagnosis of mild asthma will participate in this study (see Inclusion/Exclusion Criteria, Section 5.1 and Section 5.2). Subjects with history of severe asthma are excluded from the study.

Potential Risk of Clinical Significance	Summary of Data/Rationale for Risk	Mitigation Strategy

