### 7.1.2. Time and Events Table – Dosing visit (DV) 1 (Day 1) – DV8 (Week 8) and Early Withdrawal Visit (EW)

Procedure	Pre-dose	Dose	Post-dose				Early- Withdrawal	Notes
		0 hour	20 mins	1 hour	12 hours	24 hours		
Outpatient visit		X				X	X	Subjects get discharged 1-2 hours after dosing.
Inclusion and exclusion criteria/eligibility review	X							Only on DV1
Diary card collection and review		X					X	Collect and review diary card at every dosing visit
AE/SAE review		X					X	
Concomitant medication review		X					X	
12-lead ECG	X			X		X	X	Perform on DV1 and DV8 only. Not required at EW if this occurs during FU
Vital signs (including temperature)	X 			X 		X 	X	 Perform on DV1-8  Perform on DV1, 4 and DV8 only. Not required at EW if this occurs during FU
Laboratory assessments (include liver chemistries, haematology, clinical chemistry and urinalysis)	X					X	X	Collect samples for laboratory assessments on DV1 and DV8, Not required at EW if this occurs during FU
Blood sample for PK analysis	X		X	X				Collect samples on DV1, DV4 and DV8
Genetic sample		X						Take one sample on any of the dosing visits after genetics consent.
FeNO measurement	X							Perform FeNO measurements pre-dose on all dosing visits 1-8
Nasal examination	X					X		Conducted pre-dose at all study visits and 24 hours post-dose on DV1, DV4 and DV8

Procedure	Pre-dose	Dose	Post-dose				Early-Withdrawal	Notes
			0 hour	20 mins	1 hour	12 hours		
Nasal lavage	X						X	Collect nasal lavage samples pre-dose and 24hrs post-dose on DV1, DV4 and DV8
Blood sample for biomarker analysis	X						X	Collect blood for serum samples and PBMC preparations pre-dose and 24 hrs post-dose on DV1 and DV8
Blood sample for RNA analysis	X 						X 	PAX-gene tubes for TLR7/AFFY chip gene expression in blood collected pre-dose on DV1  and 24 hrs after DV8 
Call RAMOS	X							Randomisation will occur is at Visit 1 via the IRT. Sites should also call RAMOS at DV5.
Dispensing of study medication	X							One device will be assigned on DV1. The second device will be assigned on DV5. All devices remain in the unit.
Study drug administration		X						All doses are administered in the unit.

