11.7.3 Vital Signs

Vital Sign Parameter (Absolute)	Units	Clinical Concern Range	
		Lower	Upper
Systolic Blood Pressure	mmHg	< 85	> 160
Diastolic Blood Pressure	mmHg	< 45	> 100
Heart Rate	bpm	< 40	> 110
Body Temperature	°C	< 36.0	> 37.5

Vital Sign Parameter (Change from Baseline)	Units	Clinical Concern Range			
		Decrease		Increase	
		Lower	Upper	Lower	Upper
Systolic Blood Pressure	mmHg	≥ 20	≥ 40	≥ 20	≥ 40
Diastolic Blood Pressure	mmHg	≥ 10	≥ 20	≥ 10	≥ 20
Heart Rate	bpm	≥ 15	≥ 30	≥ 15	≥ 30
		Clinical Concern Range			
		Lower		Upper	
Body Temperature	°C	< -1		> +1	

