3.11.	All Subjects	LB4	Summary of Emergent Chemistry Results by Normal Range Criteria	ICH E3 Planned times should be each post-visit timepoint (e.g. DV1 24h, DV8 pre-dose, DV8 24h). Do not include screening visit 1 values. Use Normal Ranges for Lab tests rather than PCI ranges to determine criteria.	FSP: SAC 2

Safety: Tables					
No.	Population	IDSL / TST ID / Example Shell	Title	Programming Notes	Deliverable [Priority]
Laboratory: Haematology					
3.12.	All Subjects	LB1	Summary of Haematology Changes From Baseline	ICH E3 As per Lab Chemistry equivalent	FSP: SAC 2
3.13.	All Subjects	LB4	Summary of Emergent Haematology Results by Normal Range Criteria	ICH E3 As per Lab Chemistry equivalent	FSP: SAC 2
Laboratory: Hepatobiliary (Liver)					
3.14.	All Subjects	LIVER1	Summary of Liver Monitoring/Stopping Event Reporting	IDSL	FSP: SAC 2
ECG					
3.15.	All Subjects	EG1	Summary of ECG Findings	IDSL	FSP: SAC 2
3.16.	All Subjects	EG2	Summary of Change from Baseline in ECG Values by Visit	IDSL Include (absolute) Baseline values as the first record. Do not include Screening visit 1 values	FSP: SAC 2
Vital Signs					
3.17.	All Subjects	VS1	Summary of Change From Baseline in Vital Signs by Visit	ICH E3 Include (absolute) Baseline values as the first record. Do not include Screening visit 1 values	FSP: SAC 2
Medications					
3.18.	All Subjects	CP_CM1	Summary of Concomitant Medications by Generic Term		FSP: SAC 2
Rescue Medication					
3.19.	All Subjects	Table 10.112 TL7116958	Summary of Rescue Medication Usage	Include reasons (if easily condensed to a handful of terms). Exclude any rescue medication given as part of the BAC procedure(s) and add this as an explanatory footnote.	FSP: SAC 2

Safety: Tables					
No.	Population	IDSL / TST ID / Example Shell	Title	Programming Notes	Deliverable [Priority]
PEF					
3.20.	All Subjects	EFF_T1	Summary of Weekly Maximum PEF by Visit	Calculate the maximum PEF for the week per subject Add Appropriate Visit Column to Shell	FSP: SAC 2
3.21.	All Subjects	EFF_T1	Summary of Weekly Weighted Mean PEF by Visit	Add Appropriate Visit Column to Shell	FSP: SAC 2
Nasal Examination					
3.22.	All Subjects	SAFE_T1	Summary of Nasal Examination Data by Visit	Count as yes any entries in the free text field for Signs of Bleeding.	FSP: SAC 2

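### Heart-rate and blood-pressure change after doses 2 to 8 is measured only against Day 1; adding the 1 h change from the same visit's pre-dose value would show acute effects more sharply at little cost

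*SAP*

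**What the plan says.** The general rule in SAP 11.4.2.1 is that "the baseline value will be the latest pre-dose assessment", except where its table says otherwise. For vital signs the table does say otherwise. The row "Vital Signs (excluding body temperature" is assigned Day 1 pre-dose. Body temperature has its own row, with baseline "DV<x> Pre-Dose", the value from the corresponding dosing visit. SAP 11.4.2.2 carries these definitions into the derivations, summaries and listings unless something else is specified. No reason is given for the split.

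The protocol's dosing-visit schedule (7.1.2) collects vital signs pre-dose and at 1 h with the note "Perform on DV1-8", and at 24 h with the note "Perform on DV1, 4 and DV8 only". Protocol 7.4.4 confirms that these include pulse rate and systolic and diastolic pressure as well as temperature.

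The change is reported in Table 3.17, "Summary of Change From Baseline in Vital Signs by Visit". SAP 11.7.3, under "Vital Sign Parameter (Change from Baseline", sets limits in either direction of 15 and 30 bpm for heart rate, 20 and 40 mmHg for systolic pressure, and 10 and 20 mmHg for diastolic pressure. Listings 35 and 36 show vital signs of potential clinical importance.

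**The concern.** Protocol 4.6.1 names "increased body temperature, increased heart rate" together among the animal findings regarded as secondary to cytokine release, and 7.4.1.7 counts hypotension within 24 hours of dosing as a cytokine-related symptom. An effect that follows each dose is best seen as a change from just before that dose. The SAP does this for temperature but not for the two vital signs named beside it, although the readings needed are already collected.

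Only at DV1 is the heart-rate and blood-pressure baseline a same-day value. In the earlier 8-week study, cytokine-related fever at 80 ng appeared mainly after the second dosing visit. None was reported at 20 ng, so this is only a hint that later visits matter. At stake is how clearly a small safety data set, about 24 randomised per arm, shows an acute shift in heart rate or blood pressure, and how much of a subject's change flag reflects the dose and how much the day.

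**Working it through.** The documents give no SD, correlation or precision target for vital signs, so there is no planned figure to reproduce. Every SD and correlation below is an assumption.

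**Age of the baseline.** Doses are weekly. The gap from Day 1 is 0 weeks at DV1, 1 week at DV2 and 7 × 7 = 49 days at DV8. Seven of the eight dosing visits are affected.

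**Variance of the 1 h heart-rate change, day-plus-error model.** Let b be the between-day SD and w the within-visit SD, in bpm. Against Day 1, SD = √(2(b² + w²)). Against the same visit's pre-dose value, SD = √2 × w. The variance ratio is (b² + w²)/w².

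| b, w | SD against Day 1 | SD same visit | Variance ratio |
|---|---|---|---|
| 4, 4 | √64 = 8.0 | 5.7 | 32/16 = 2.0 |
| 6, 4 | √104 = 10.2 | 5.7 | 52/16 = 3.25 |
| 6, 5 | √122 = 11.0 | 7.1 | 61/25 = 2.4 |
| 8, 5 | √178 = 13.3 | 7.1 | 89/25 = 3.6 |

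Under normality and no drug effect, the chance of a rise of 15 bpm or more at one visit is 3% to 13% against Day 1 and 0.4% to 1.7% against the same visit. With 24 per arm, the standard error of the arm difference, SD × √(2/24), is 2.3 to 3.9 bpm and 1.6 to 2.0 bpm respectively.

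**The same question in correlations.** SD of change = SD × √(2(1 − r)), with r_w for same-day readings and r_b for readings at different visits. The variance ratio is (1 − r_b)/(1 − r_w):

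- r_w/r_b = 0.9/0.7: 0.3/0.1 = 3.0
- 0.85/0.6: 0.40/0.15 = 2.7
- 0.8/0.5: 0.5/0.2 = 2.5
- 0.8/0.7: 0.3/0.2 = 1.5
- 0.7/0.7: 1, so no gain

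The two models together give about 1.5 to 3.6 wherever r_w exceeds r_b.

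**Flags with no drug effect**, at the lower limit and in either direction, 2(1 − Φ(limit/SD of change)), for r_w/r_b from 0.9/0.7 to 0.8/0.5. The last column is a simulation of the 1 h readings at DV2 to DV8.

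| Sign, limit, assumed SD | Per visit: same visit / Day 1 | Any flag DV2–DV8: same visit / Day 1 |
|---|---|---|
| Heart rate, 15 bpm, SD 8–12 | 0.0–4.8% / 1.5–21% | 0–29% / 8–69% |
| Systolic, 20 mmHg, SD 10–14 | 0.0–2.4% / 1.0–15% | 0–16% / 5–56% |
| Diastolic, 10 mmHg, SD 7–9 | 0.1–7.9% / 6.5–27% | 1–44% / 29–79% |

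If r_w = r_b = 0.7, the per-visit rates are equal. The any-visit rate is then slightly higher for the same-visit change (heart rate at SD 10: 31% against 24%), because the Day 1 changes share one baseline reading.

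**Precision.** For heart rate at SD 10 bpm with 20 completers per arm, the 95% half-width is 1.96 × SD of change × √(2/20). That gives 2.8 bpm (SD of change 4.5) to 3.9 bpm (6.3) for the same-visit change, and 4.8 bpm (7.7) to 6.2 bpm (10.0) for the Day 1 change.

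**The case against.** The case for leaving the rule alone is substantial, and much of it stands.

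- **No bias between arms.** Drift common to both arms cancels against placebo. If Table 3.17 includes pre-dose rows at each visit, the mean acute change follows by subtraction. A reader might infer that the plan cannot separate an acute effect from drift; for means that goes too far. What subtraction does not recover is the spread of the individual changes or the subject-level flags.
- **Flags are not compared by arm.** Values of potential clinical importance appear only in listings, which SAP 8.2.3 places under absolute values, and the absolute limits do not depend on baseline. A reader might infer that noise flags would dilute a real excess on drug, but no planned count of flags by arm exists to be diluted.
- **Temperature may deserve its own rule.** It has a documented, transient, dose-related rise in humans (at most 0.34°C at 20 ng). The heart-rate finding is from animals without stated timing, and no hypotension was reported in the earlier study. This may explain the split, though the SAP does not say so.
- **Day 1 is needed.** SAP 11.3.1 assumes that treatment effects last a week, the whole dosing interval, so pre-dose values at DV2 to DV8 are on treatment. Replacing Day 1 could miss events. A subject 10 bpm above Day 1 before dosing who gains 10 bpm at 1 h is at +20 and is flagged now; against separate baselines each step is 10, below the limit of 15. This rules out replacement but not addition.
- **24 h readings.** These are taken the next day. Under the day-plus-error model their change has SD √(2(b² + w²)), the same as against Day 1, so the gain is confined to 1 h.
- **First-visit anxiety.** A reader might suspect that Day 1 values are inflated by it, but two screening visits and a next-day return precede DV1.

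**Conclusion.** The point holds as a modest loss of information. The plan's only heart-rate and blood-pressure change uses a baseline up to 49 days old at seven of eight dosing visits, while a same-day value is collected and not used as a baseline. The 1 h change is noisier than it need be, with variance about 1.5 to 3.6 times larger, and subject-level change flags mix the response to the dose with variation between visits.

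The size rests wholly on assumed SDs and correlations. The direction rests on one condition: readings taken about an hour apart must correlate better than readings taken weeks apart. If they do not, there is no gain. DV1, the absolute limits and the cytokine-symptom tables are unaffected. The documents do not support a stronger conclusion that the safety comparison is invalid or that the Day 1 baseline is wrong.

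**What to change.** Keep Day 1 pre-dose as the baseline for heart rate and blood pressure in SAP 11.4.2.1, with its change flags, so that a sustained or cumulative shift remains visible. Leave the temperature rule as it is. Then:

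- Add a second baseline for heart rate, systolic and diastolic pressure: the same dosing visit's pre-dose value, used for the 1 h reading at DV1 to DV8.
- Add a block to Table 3.17 with this 1 h change by visit and arm.
- Apply the existing change limits in 11.7.3 to this change as well, and show in Listings 35 and 36 which baseline triggered each flag.

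The SAP has a precedent. For TLR7 blood biomarkers, 11.5.5 computes fold changes against both DV1 pre-dose and the visit's own pre-dose value, and figure type PD_F5 in 8.4.2 displays the two as separate rows.

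No new data are needed. The cost is one display block and some additional flags to review. With no drug effect and under the flag-table assumptions, the same-visit change would be flagged at up to 4.8% of visits for heart rate, 2.4% for systolic and 7.9% for diastolic pressure; some of these readings would already be flagged against Day 1.
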